5. DETERMINATION OF SAMPLE SIZE

A sample size of 30 subjects is planned for this trial to provide a sizeable number of subjects to support the following projections. The primary efficacy endpoint will be demonstrated to be statistically greater than 20% if at least 12/30 (40%) responders are observed. In that case, the

lower bound of a 95% confidence interval (CI) for the proportion of responders will be approximately 23%.

6. GENERAL ANALYSIS CONSIDERATIONS

The statistical analyses will be reported using summary tables, listings, and figures (TLFs). The International Council for Harmonisation (ICH) numbering convention will be used for all TLFs. Unless otherwise noted, all statistical testing will be 2-sided and will be performed at the 0.05 significance level.

Continuous variables will be summarized by presenting the number of observations, means, standard deviations (SDs), medians, quartiles, minimums, and maximums.

Categorical variables will be summarized by presenting counts and percentages of subjects in corresponding categories. All possible categories as defined in the CRF should be populated, even if they have zero counts. Percentages are based on the total number of subjects unless otherwise specified.

All summary tables will be presented by cohort and with an overall column. If Cohort 2 enrolls both subjects with previous mild IR and those with no previous IR, then the data will be summarized by IR category (no IR, mild IR) within Cohort 2 and for Cohorts 1 and 2 no IR subjects combined.

Individual subject data obtained from the eCRFs, external vendors, and any derived data will be presented by subject in data listings.

The analyses described in this plan are considered a priori, in that they have been defined before database lock.

Any analyses performed after database lock will be considered post hoc and exploratory. Post hoc analyses will be labeled as such on the output and identified in the CSR.

All analyses and tabulations will be performed using SAS® software Version 9.4 or higher. Tables, listings, and figures will be presented in RTF format.

7. VISIT WINDOWS

For all analyses, data will be summarized according to the scheduled visit and time points as outlined in the protocol and by the visit denoted on the eCRF. The reference date associated with each visit is collected on the Visit Date eCRF page. Further, the End of Study/Early Termination (ET) visit and the End of Pegloticase Infusion Visit will be windowed to a visit based on the study day of occurrence relative to the target day of each scheduled visit according to Table 1, Table 2, Table 3, Table 4, Table 5, Table 6, Table 7, and Table 8 below. If an End of Study/ET or End of Pegloticase Infusion visit is reassigned to a visit for which the subject has scheduled data collected, the data from the nominal scheduled visit will take precedence and the data from

the End of Study/ET or End of Pegloticase Infusion visit will not be summarized. Table 1 shows windows for the vital sign assessments. Table 2 shows windows for the hematology, chemistry, and urinalysis clinical laboratory assessments. Table 3 shows the windows for the hsCRP laboratory assessments. Table 4 shows the windows for the DECT scans. Table 5 shows the windows for HAQ and CCI count assessments. Table 6 shows the windows for CCI [REDACTED], and CCI [REDACTED]. Table 7 shows the windows for CCI [REDACTED] and CCI [REDACTED] assessments. Table 8 shows the windows for sUA assessments. Unscheduled sUA visits, assessed by the central or local laboratory, will also be assigned to an analysis visit according to the windows in Table 8. These unscheduled assessments will only be used for the determination of sUA responder status. For all assessments, the study day in the Pegloticase + MTX period will be calculated relative to the first dose of pegloticase.

Table 1: Visit Windows for Assigning End of Study/ET and End of Pegloticase Visits to a Scheduled Visit (Vital Signs)

Study Period	Visit	Target Day	Window for Reassignment to Scheduled Visit (days)
Pegloticase + MTX	Day 1	1	1
	Week 2	15	2 – 22
	Week 4	29	23 – 36
	Week 6	43	37 – 50
	Week 8	57	51 – 64
	Week 10	71	65 – 78
	Week 12	85	79 – 92
	Week 14	99	93 – 106
	Week 16	113	107 – 120
	Week 18	127	121 – 134
	Week 20	141	135 – 148
	Week 22	155	149 – 162
	Week 24	169	163 – 176
	Week 26	183	177 – 190
	Week 28	197	191 – 204
	Week 30	211	205 – 218
	Week 32	225	219 – 232
	Week 34	239	233 – 246
	Week 36	253	247 – 260
	Week 38	267	261 – 274
	Week 40	281	275 – 288
	Week 42	295	289 – 302
	Week 44	309	303 – 316
	Week 46	323	317 – 330

Study Period	Visit	Target Day	Window for Reassignment to Scheduled Visit (days)
	Week 48	337	≥331

Table 2: Visit Windows for Assigning End of Study/ET and End of Pegloticase Visits to a Scheduled Visit (Hematology and Chemistry Laboratory Assessments, eGFR, urine albumin:creatinine ratio)

Study Period	Visit	Target Day	Window for Reassignment to Scheduled Visit (days)
Pegloticase + MTX	Day 1	1	1
	Week 2	15	2 – 29
	Week 6	43	30 – 71
	Week 14	99	72 – 134
	Week 24	169	135 – 211
	Week 36	253	212 - 295
	Week 48	337	≥296

Table 3: Visit Windows for Assigning End of Study/ET and End of Pegloticase Visits to a Scheduled Visit (hsCRP)

Study Period	Visit	Target Day	Window for Reassignment to Scheduled Visit (days)
Pegloticase + MTX	Day 1	1	1
	Week 14	99	2 – 134
	Week 24	169	135 – 211
	Week 36	253	212 – 295
	Week 48	337	≥296

Table 4: Visit Windows for Assigning End of Study/ET and End of Pegloticase Visits to a Scheduled Visit (DECT)

Study Period	Visit	Target Day	Window for Reassignment to Scheduled Visit (days)
Pegloticase + MTX	Day 1	1	1
	Week 14	99	2 – 134
	Week 24	169	135 – 253
	Week 48	337	≥254

Table 5: Visit Windows for Assigning ET and End of Pegloticase Visits to a Scheduled Visit (HAQ, CCI [REDACTED])

Study Period	Visit	Target Day	Window for Reassignment to Scheduled Visit (days)
Pegloticase + MTX	Day 1	1	1
	Week 6	43	2 – 71
	Week 14	99	72 – 120
	Week 20	141	121 – 155
	Week 24	169	156 – 211
	Week 36	253	212 – 295
	Week 48	337	≥296

Table 6: Visit Windows for Assigning ET and End of Pegloticase Visits to a Scheduled Visit (CCI [REDACTED], CCI [REDACTED])

Study Period	Visit	Target Day	Window for Reassignment to Scheduled Visit (days)
Pegloticase + MTX	Day 1	1	1

Study Period	Visit	Target Day	Window for Reassignment to Scheduled Visit (days)
	Week 14	99	2 – 134
	Week 24	169	135 – 211
	Week 36	253	212 – 295
	Week 48	337	≥296

Table 7: Visit Windows for Assigning ET and End of Pegloticase Visits to a Scheduled Visit
 (CCI [REDACTED], CCI [REDACTED])

Study Period	Visit	Target Day	Window for Reassignment to Scheduled Visit (days)
Pegloticase + MTX	Day 1	1	1
	Week 2	15	2 – 29
	Week 6	43	30 – 71
	Week 14	99	72 – 127
	Week 22	155	128 – 162
	Week 24	169	163 – 211
	Week 36	253	212 – 295
	Week 48	337	≥296

Table 8: Visit Windows for Assigning ET and End of Pegloticase Visits to a Scheduled Visit (sUA Assessments)

Study Period	Visit	Target Day	Window for Reassignment to Scheduled Visit (days)
Pegloticase + MTX	Day 1	1	1
	Week 2	15	2 – 22
	Week 4	29	23 – 36
	Week 6	43	37 – 50
	Week 8	57	51 – 64
	Week 10	71	65 – 78
	Week 12	85	79 – 92
	Week 14	99	93 – 106
	Week 16	113	107 – 120
	Week 18	127	121 – 134
	Week 20	141	135 – 144
	Week 21	148	145 – 151
	Week 22	155	152 – 158
	Week 23	162	159 – 165
	Week 24	169	166 – 176
	Week 26	183	177 – 190
	Week 28	197	191 – 204
	Week 30	211	205 – 218
	Week 32	225	219 – 232
	Week 34	239	233 – 246
	Week 36	253	247 – 260
	Week 38	267	261 – 274
	Week 40	281	275 – 288
	Week 42	295	289 – 302
	Week 44	309	303 – 316
	Week 46	323	317 – 330
	Week 48	337	≥331

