9.5.4.7 Clinical Laboratory Safety Tests

A blood sample for G6PD analysis will be collected at the Screening Visit. G6PD testing should be performed by the central laboratory; however, if performed by the local laboratory, normal ranges should be provided.

Blood samples (for hematology and clinical chemistry) will be collected at the Screening Visit; at the Week -2 Visit; prior to the pegloticase infusion on Day 1 and at the Weeks 2, 6 and 14 Visits (Pegloticase + MTX Treatment Period); prior to pegloticase infusion at the Week 24 and 36 Visits (subjects who may gain further benefit beyond 12 infusions and elect to receive pegloticase + MTX during the Optional Pegloticase + MTX Extension Period); and at the End of Pegloticase (if applicable) or Week 24 or 48/End of Trial/Early Termination Visits.

Urine samples (for albumin:creatinine ratio) will be collected at the Screening Visit; prior to the pegloticase infusion on Day 1 and at the Weeks 2, 6 and 14 Visits (Pegloticase + MTX Treatment Period); prior to pegloticase infusion at the Week 24 and 36 Visits (subjects who may gain further benefit beyond 12 infusions and elect to receive pegloticase + MTX during the Optional Pegloticase + MTX Extension Period); and at the End of Pegloticase (if applicable) and Week 24 or 48/End of Trial/Early Termination Visits.

Women of childbearing potential (as defined in [Section 9.5.4.2](#)) will have a serum pregnancy test at the Screening Visit; urine samples (for human chorionic gonadotropin) will be collected at all other visits.

Safety laboratory assessments will include:

- Hematology: complete blood count (hemoglobin concentration, hematocrit, erythrocyte count, platelet count, leukocyte count, and differential leukocyte count) with differential;
- Chemistry: albumin, transaminases (AST, ALT), alkaline phosphatase, total bilirubin, creatinine (including calculation for eGFR calculated by the MDRD equation: $175 \times (\text{standardized serum creatinine } [\text{mg/dL}]^{-1.154} \times (\text{age})^{-0.203} \times (0.742 \text{ if female}) \times (1.212 \text{ if African American}) \text{ or } 175 \times (\text{standardized serum creatinine } [\mu\text{mol/L}]^{88.4})^{-1.154} \times (\text{age})^{-0.203} \times (0.742 \text{ if female}) \times (1.212 \text{ if African American})$), glucose, sodium, potassium, calcium, chloride, total protein and blood urea nitrogen; and

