9.5.8.4 End of Pegloticase Visit

Subjects who end pegloticase infusions prior to Week 22 will complete the End of Pegloticase Visit procedures within 2 weeks of their final infusion. Subjects are especially encouraged to complete trial visits at the trial site for key efficacy and safety assessments at Weeks 10, 12, 14, 20, 21, 22, 23 and 24/End of Trial/Early Termination, so that sUA and other key assessments can be completed. During visits between these key efficacy and safety collection visits, in subjects who have stopped infusions, subjects may complete trial visits in person or via a telephone visit to collect AE, concomitant medication and gout flare information (see [Section 9.3.3.1.1](#)).

For subjects who agree to continue trial visits after the End of Pegloticase Visit, the 30-Day Post Treatment Follow-up Visit will be captured as part of the continued visits; however, if the last trial visit is <30 days posttreatment, the 30-Day Post-Treatment Follow-up phone call/email will still be required.

The following procedures will be completed at the End of Pegloticase Visit:

- Principal Investigator review of subject clinical status and treatment goals.
- Perform a targeted physical examination (at a minimum this should include heart, lungs and abdominal examination).
- Document gout flares and intensity.
- Record vital signs (blood pressure, respiratory rate, temperature and heart rate) prior to discharge (see [Section 9.5.4.4](#)).
- Obtain a urine sample for pregnancy testing from female subjects of childbearing potential.
- Obtain optional serum and urine samples from subjects who consent for future analysis.
- Obtain blood samples for hematology, clinical chemistry and hs-CRP analysis and eGFR calculation (calculated by the central laboratory).
- Obtain a urine sample for albumin:creatinine ratio.

- Obtain a blood sample (1 sample) for measurement of sUA.
- Administer MTX (subjects who have not stopped pegloticase due to individual subject sUA discontinuation criteria).
- Assess MTX compliance/reconciliation.
- **CCI** [REDACTED].
- Administer HAQ-DI, **CCI** [REDACTED]
- Record **CCI** [REDACTED].
- If handheld uric acid device is provided, assess Investigator or subject user experience with uric acid device questionnaire at any time during the visit prior to discharge from the site.
- Assess MTX compliance.
- Ask Yes/No question regarding folic acid compliance.
- Ask Yes/No question regarding gout flare prophylaxis compliance.

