14.4 Clinical Laboratory Evaluation

A central laboratory will be used for protocol-specified clinical laboratory parameters. Laboratory parameters (chemistry, hematology, and urinalysis) will be summarized in conventional units using descriptive statistics at baseline and at each post-baseline time point. Changes from baseline will also be summarized for all continuous parameters. Summaries will be presented for change from methotrexate baseline (last assessment prior to the first dose of MTX in the MTX Run-in Period) and change from pegloticase baseline (last assessment prior to the first dose of pegloticase). The following laboratory parameters will be summarized:

- Hematology: hemoglobin, hematocrit, erythrocytes, leukocytes, neutrophils/leukocytes, lymphocytes/leukocytes, monocytes/leukocytes, eosinophils/leukocytes, basophils/leukocytes, platelets.
- Chemistry: albumin, aspartate aminotransferase, alanine aminotransferase, alkaline phosphatase, total bilirubin, creatinine, glucose, sodium, potassium, calcium, chloride, total protein, blood urea nitrogen, hs-CRP.
- Urinalysis: albumin:creatinine ratio.

If a continuous laboratory value is reported as either below or above the limits of quantification, the qualifiers will be dropped and the numeric value used in the analysis (e.g., “< 3” will be summarized as “3” and “> 200” will be summarized as “200”).

Shift tables for laboratory parameters by Common Terminology Criteria for Adverse Events (CTCAE) grade will be presented by visit for those laboratory parameters with CTCAE v5.0 grade defined.

A summary of subjects with elevated liver function tests (aspartate aminotransferase, alanine aminotransferase, alkaline phosphatase, and total bilirubin) and subjects who possibly meet Hy's law criteria will also be provided by visit and overall.

All laboratory tests will be listed, and results will be categorized as low, normal, or high based on their normal ranges. Separate listings of out-of-range results will also be presented.

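### SAP 7 leaves End of Pegloticase safety labs out of the by-visit laboratory tables in at least half of the possible stopping patterns, and SAP 14.4 describes no worst post-baseline CTCAE shift that would pick them up

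*SAP*

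**What the plan says.** Protocol 9.5.8.4 sets an End of Pegloticase visit for early stoppers: "Subjects who end pegloticase infusions prior to Week 22 will complete the End of Pegloticase Visit procedures within 2 weeks of their final infusion". The procedures there include: "Obtain blood samples for hematology, clinical chemistry and hs-CRP analysis and eGFR calculation". Protocol 9.5.4.7 places the scheduled on-treatment hematology and chemistry samples "prior to the pegloticase infusion on Day 1 and at the Weeks 2, 6 and 14 Visits", with Week 24 as the next time point.

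SAP 7 assigns the End of Pegloticase and early-termination visits to a scheduled visit by study day. Table 2 gives the windows for "Hematology and Chemistry Laboratory Assessments, eGFR, urine albumin:creatinine ratio": Week 2 is Days 2–29, Week 6 is Days 30–71, Week 14 is Days 72–134 and Week 24 is Days 135–211. The precedence rule reads "If an End of Study/ET or End of Pegloticase Infusion visit is reassigned to a visit for which the subject has scheduled data collected", the scheduled result is kept and the data from "the End of Study/ET or End of Pegloticase Infusion visit will not be summarized". Unscheduled results are given a visit for sUA only.

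SAP 14.4 then states: "Shift tables for laboratory parameters by Common Terminology Criteria for Adverse Events (CTCAE) grade will be presented by visit". It also plans listings of all laboratory results, separate out-of-range listings, and a summary of liver-test elevations and possible Hy's law cases that is both by visit and overall. It does not describe a shift to worst post-baseline grade.

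**The concern.** The protocol deliberately collects safety labs shortly after pegloticase stops. The SAP then uses them in the tables only if the subject has no scheduled sample in the same window. Because few lab visits are scheduled, each window is long and a scheduled sample is usually present or due. When the two collide, the row shows a sample from another time: either before the stop or some weeks after it. As the shift tables are by visit, a CTCAE grade reached only at the End of Pegloticase visit then has no place in them. With about 30 subjects planned, one or two such results can change how a shift table reads.

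**Working it through.** **Reproducing the windows.** The lab target days are 15, 43, 99, 169, 253 and 337. The midpoints are (15+43)/2 = 29, (43+99)/2 = 71, (99+169)/2 = 134, (169+253)/2 = 211 and (253+337)/2 = 295. These match the upper bounds in Table 2 exactly. The four main-period windows after Day 1 are therefore 28, 42, 63 and 77 days wide.

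**Inputs.** Possible last infusions before Week 22 are numbers k = 1 to 11, on nominal Day L = 1 + 14(k − 1). The End of Pegloticase visit falls on Day L+1 to L+14. That gives 11 × 14 = 154 combinations.

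**Rule applied.** Find the Table 2 window containing the visit day and take its target day T.
- If T ≤ L, the scheduled sample has already been drawn, so exclusion is certain.
- If T > L and T is not the visit day, the result is excluded only if the sample due at T is drawn.
- If T is the visit day, the two visits coincide.

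| Last infusion (week) | L | Visit days | Window (T) | Outcome |
|---|---|---|---|---|
| 1 (Day 1) | 1 | 2–15 | Week 2 (15) | 13 conditional, 1 coincides |
| 2 (Week 2) | 15 | 16–29 | Week 2 (15) | 14 certain |
| 3 (Week 4) | 29 | 30–43 | Week 6 (43) | 13 conditional, 1 coincides |
| 4 (Week 6) | 43 | 44–57 | Week 6 (43) | 14 certain |
| 5 (Week 8) | 57 | 58–71 | Week 6 (43) | 14 certain |
| 6 (Week 10) | 71 | 72–85 | Week 14 (99) | 14 conditional |
| 7 (Week 12) | 85 | 86–99 | Week 14 (99) | 13 conditional, 1 coincides |
| 8 (Week 14) | 99 | 100–113 | Week 14 (99) | 14 certain |
| 9 (Week 16) | 113 | 114–127 | Week 14 (99) | 14 certain |
| 10 (Week 18) | 127 | 128–134 | Week 14 (99) | 7 certain |
| 10 (Week 18) | 127 | 135–141 | Week 24 (169) | 7 conditional |
| 11 (Week 20) | 141 | 142–155 | Week 24 (169) | 14 conditional |

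**Totals.**
- Certain: 5 × 14 + 7 = 77, and 77/154 = 50%.
- Adding those conditional on Week 14 labs (14 + 13 = 27) and on Week 24 labs (7 + 14 = 21): 77 + 27 + 21 = 125, and 125/154 = 81%. Protocol 9.3.3.1.1 keeps stopped subjects in the trial to Week 24 and singles out Weeks 14 and 24 among the visits they are urged to attend.
- Adding those conditional on Week 2 and Week 6 labs (13 + 13): 151/154 = 98%. This is an upper figure, because the same section allows those visits by telephone once infusions have stopped.

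**Stops under the sUA rule** (last infusion at Weeks 2 to 12, 6 × 14 = 84 combinations): 42 certain (50%), and 42 + 27 = 69 (82%) with Week 14 labs drawn.

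**Sensitivity.** Protocol 9.5.4.7 links End of Pegloticase and Week 24/48 blood sampling with 'or', while Protocol 9.5.8.6 has early stoppers complete the Week 24 labs. If the 'or' is read as no Week 24 labs for them, the figure with Week 14 attended is 77 + 27 = 104, and 104/154 = 68%.

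**Which sample is kept.** A Day 71 result after infusion 5 yields to the Day 43 sample, 28 days earlier. A Day 72 result after infusion 6 yields to the Day 99 sample, 28 days after the last infusion. The retained value can lie on either side of the stop.

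**The case against.** The strongest reply is that little is lost. All results are listed, out-of-range results are listed separately, and a trial of about 30 subjects can be reviewed from listings. A clinically significant abnormality is reportable as an adverse event under Protocol 9.5.4.1.1.1, and SAP 14.2 tabulates events by maximum Rheumatology CTC grade using onset date, not the SAP 7 windows. Liver-test elevations may enter the overall summary. Protocol 9.6.7 asks for laboratory results by trial visit, and the Week 2, 6 and 14 rows correctly show what was drawn at those visits. For 42 of the 77 certain exclusions (infusions 2, 4 and 8), the retained sample was drawn on the day of the last infusion, 1 to 14 days before the End of Pegloticase visit.

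Most of this stands, and it limits the point to the laboratory tables. Two gaps remain. Adverse-event capture depends on the investigator judging a change clinically significant, whereas a shift table does not. SAP 14.4 also does not say whether the overall liver summary is exempt from the precedence rule, and it covers liver tests only. Appendix C's table list is blacked out, so it cannot be checked for a worst-grade table; the text of 14.4 describes none.

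A reader might infer that the rule replaces abnormal stop values with earlier normal ones and so hides toxicity. The documents do not support that: the retained sample is sometimes later, and nothing shows it would be normal. A reader might also infer that most stops are driven by toxicity. The protocol gives no frequencies. Its numeric stopping rule concerns sUA response, and Protocol 9.4.1.1 with Table 9.2 handles MTX toxicity by changing MTX while pegloticase may continue.

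**Conclusion.** The point holds as a gap in the laboratory tables. End of Pegloticase labs are excluded for certain after last infusions 2, 4, 5, 8 and 9 and on half of the visit days after 10: 50% of combinations, and 81% if Week 14 and Week 24 labs are drawn. After infusions 1, 3, 6, 7, 11 and late 10 the result is kept if the later scheduled sample is missed.

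The percentages assume nominal visit days, equal weight for every stopping time and visit day, and that earlier scheduled labs were drawn; the documents give no distribution of stopping times. They apply to the Table 2 parameters only, not to hs-CRP, which has its own windows.

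The direction and size of any bias are not known. No trial decision depends on these tables: the tolerability criteria use severe infusion reactions and anaphylaxis, and the primary endpoint is based on sUA. This is a worthwhile and cheap improvement, not a threat to the trial's conclusions.

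**What to change.** In SAP 14.4, add a shift table from baseline to worst post-baseline CTCAE grade, and state that it uses every post-baseline result: scheduled, End of Pegloticase, early termination and unscheduled. State that the overall part of the liver-test and Hy's law summary uses the same set, and add to SAP 7 that the precedence rule governs by-visit rows only. Optionally, show End of Pegloticase/early termination as its own row in the by-visit laboratory tables.

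The cost is SAP wording, one extra table and, if chosen, one extra row. No new samples or visits are needed, and no clinical rule changes.

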8. ANALYSIS SETS

The following subject analysis sets will be used for safety analyses:

- The safety analysis set will include all enrolled subjects who receive at least 1 dose of pegloticase + MTX.
- The MTX analysis set will include all subjects who receive at least 1 dose of MTX.

The following subject analysis set will be used for efficacy analyses:

- The intent-to-treat (ITT) analysis set will include all enrolled subjects who receive at least 1 dose of pegloticase + MTX.

The following analysis set will be used for **CCI**

- **CCI**

Note that the safety analysis set and ITT analysis set are defined the same for this protocol.

